6.1.3. Dose Modification Guidelines

6.1.3.1. Dose Reduction

Patients who experience a KZR-616-related AE at the 45 mg dose are permitted to undergo dose reduction to 30 mg KZR-616 for subsequent doses at the discretion of the Investigator, in consultation with the Medical Monitor. Written approval from the Medical Monitor should be obtained in advance of implementing dose reduction, when possible. After dose reduction is implemented, patients should remain on 30 mg KZR-616 for at least 2 doses, after which the dose may be re-escalated to 45 mg. If the 45-mg dose is not tolerated after re-escalation, the 30-mg dose may be continued for the remainder of the study, or re-escalation to 45 mg may be re-attempted after written approval from the Medical Monitor. Any dose modifications should be documented in the electronic case report form (eCRF) as per [Section 9.1.4](#).

6.1.3.2. Missed Doses

Doses should be administered within the visit windows as per the Schedule of Assessments ([Section 7.1](#)). Any doses administered outside of the visit window will be considered a protocol deviation; however, if necessary to avoid missing a dose, doses may be administered up to 3 days from the date of scheduled administration with a minimum of 4 days required between doses.

Patients who meet individual patient stopping rules ([Section 8.1.2](#)) may resume dosing after discussion between the Investigator and Medical Monitor. Upon resumption of dosing, subsequent doses should be timed according to the original dosing schedule based on Day 1. Missed doses should be documented in the eCRF as per [Section 9.1.4](#). Patients who are discontinued for missed doses should have their discontinuation recorded in the eCRF based on the reason the doses were missed, eg, AE, protocol noncompliance (see [Section 8.2](#)).

If KZR-616 is permanently discontinued due to an AE, the planned assessments (see Schedule of Assessments in [Table 1](#)) should continue for the protocol-specified time period. If the patient cannot continue with the planned assessments, the Early Termination Visit (ETV) should be accomplished at a minimum (see [Section 8.2](#)).

6.2. Prior and Concomitant Treatments

Any concomitant therapies must be recorded on the eCRF. A concomitant therapy is any therapy that may be used, eg, physical therapy, surgery, or medication. A concomitant medication is any prescription or over-the-counter preparation, including vitamins and supplements. Concomitant medication use will be recorded until the last follow-up visit. Details to be recorded include, but are not limited to, the concomitant medication generic name, dose, route, frequency of administration, and indication.

6.2.1. Permitted Concomitant Medications

6.2.1.1. Myositis Disease-related Concomitant Medications

Immunosuppressant and corticosteroid dose and frequency may be reduced at the Investigator's discretion (see [Section 6.2.1.1.1](#) regarding optional tapering of oral corticosteroids). If a concomitant treatment for myositis is decreased or discontinued, the reason must be documented in the eCRF.

If an Investigator determines that a patient needs additional medication for treatment of myositis, the Medical Monitor should be informed; if possible, a discussion should occur between the Investigator and Medical Monitor prior to implementation of the additional medication. If a concomitant treatment for myositis is added, the reason must be documented in the eCRF.

6.2.1.1.1. Optional Tapering of Oral Corticosteroids

Tapers of concomitant oral corticosteroids are optional and may be initiated at the Investigator's discretion. Patients with well-controlled disease, in the Investigator's opinion, may be considered for tapers (eg, those with no, minimal, or stable active disease based on overall evaluation of activity such as weakness, myalgia, rash, CK and other assessments). There is no protocol-defined, mandatory tapering schedule. Possible schedules for gradual tapering of prednisone or prednisone equivalents in the setting of myositis include:

- Taper current dose by 5 mg/day every 12 weeks until 10 mg/day, then by 2.5 mg/day every 12 weeks until discontinued or worsening of disease requires an increase, in the Investigator's opinion.
- For a slower taper from 5 mg/day until discontinuation or worsening of disease:
From 5 mg/day dose, taper by 1-2.5 mg/day every 12 weeks until discontinued or worsening of disease requires an increase, in the Investigator's opinion.

6.2.1.2. Other Concomitant Therapies

Other concomitant therapies for comorbid conditions (eg, antihypertensives or lipid lowering agents) are permitted; these therapies should be recorded in the eCRF. Details regarding physical therapy, occupational therapy, or exercise should also be recorded in the eCRF.

6.2.1.3. Potential Drug-Drug Interactions

KZR-616 should be administered at least 6 hours before, or 4 hours after, drugs that are known inhibitors of P-gp (eg, cyclosporine [not permitted during the study], atorvastatin, azithromycin, colchicine, omeprazole).

6.2.1.4. Vaccinations

It is strongly recommended that patients be up to date on immunizations per current 2015 American College of Rheumatology (ACR) guidelines ([Singh 2016](#)). Vaccinations received at any time during the study should be recorded in the eCRF. Live vaccinations are not permitted during the study. If vaccination against herpes zoster is required during the study, Shingrix or

other non-live vaccine (if available) is preferred over live vaccines. Similarly, vaccination against influenza virus with inactivated vaccine is preferred.

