2.2. Study Endpoints

2.2.1. Efficacy Endpoints

- Mean change in TIS over time for all patients, for patients with DM only, for patients with PM only, and for patients with a myositis-associated antibody or myositis-specific antibody at the Screening Visit of Study KZR-616-003
- Proportion of patients by TIS response (minimal response = TIS \geq 20, moderate response = TIS \geq 40, major response = TIS \geq 60)
- Proportion of patients meeting IMACS definition of improvement (DOI) over time for patients with baseline core set measures as ascertained at the beginning of KZR-616-003
- Mean change and mean percentage change over time in the IMACS individual CSAMs and CSDMs, stratified by all patients and patients with myositis-associated or myositis-specific antibody at the Screening Visit of Study KZR-616-003
- Mean change over time in the Cutaneous Dermatomyositis Disease Area and Severity Index (CDASI) for all patients with DM, and for patients with DM who have active skin manifestations at baseline of Study KZR-616-003E
- Mean change over time in the MDI
- Mean change over time in muscle enzymes
- Change in proportion and dose of corticosteroid and non-corticosteroid immunosuppressants during Study KZR-616-003E for all patients, and for patients taking corticosteroids or non-corticosteroid immunosuppressants at baseline of Study KZR-616-003E
- Percentage of patients requiring additional medication for myositis treatment during Study KZR-616-003E
- Mean change over time in the EuroQol 5-dimension 5-level (EQ-5D-5L)
- Additional exploratory endpoints (Physician Global Impression of Change [MDGIC], Functional Index-2 [FI-2], Patient Global Impression of Change [PGIC], and Peak Pruritis Numerical Rating Scale [NRS]) will be assessed at multiple time points

As KZR-616-003E is an open-label extension study, additional exploratory endpoints may be conducted, and will be described in the final statistical analysis plan (SAP). Efficacy endpoints may include treatment periods that include data from Study KZR-616-003 based on treatment sequence in that study. See [Section 10](#) for additional details of statistical analyses.

All endpoints, except where noted, will include analyses of all patients, those with DM only, and those with PM only.

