6.2.2. Other Restrictions and Prohibitions

For patients requiring surgery, or for any planned surgery during the study, the Medical Monitor should be consulted to discuss KZR-616 dosing.

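### Section 6.2.1.4 bans live vaccines during the study, yet its zoster sentence ranks a live vaccine as a second choice

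*Combined protocol and SAP*

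**What the plan says.** All the vaccine rules are in Section 6.2.1.4 of the protocol. It opens with encouragement: "It is strongly recommended that patients be up to date on immunizations". It then asks for documentation: "Vaccinations received at any time during the study should be recorded in the eCRF". Next comes the prohibition, with no exception attached: "Live vaccinations are not permitted during the study".

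The zoster sentence follows directly. It opens with the condition "If vaccination against herpes zoster is required during the study" and goes on to say that Shingrix or "other non-live vaccine (if available) is preferred over live vaccines". The section closes by saying that, in the same way, "vaccination against influenza virus with inactivated vaccine is preferred".

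**The concern.** A prohibition and a preference are different kinds of instruction. The first removes live vaccines from the choices open to a site. The second puts them below non-live vaccines but leaves them on the list. Both are given for the same period, one straight after the other.

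A site that asks what to do about zoster will look to the zoster sentence, because it is the more specific of the two. In good faith, it could take a live product to be acceptable when a non-live one is hard to obtain. Giving it would breach the ban while arguably following the next sentence.

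The question can arise in practice. The section itself urges current immunization, and the efficacy endpoints in Section 2.2.1 provide for "patients taking corticosteroids or non-corticosteroid immunosuppressants at baseline", so some patients may have background immunosuppression when the choice of vaccine is made. At stake are a clear safety instruction and consistent conduct across sites.

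**Working it through.** The plan gives no figure to reproduce, and the central question needs no arithmetic. It is whether the sentences can all be followed together.

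1. **Period.** The ban ("Live vaccinations are not permitted during the study") and the zoster condition ("If vaccination against herpes zoster is required during the study") both apply during the study. They cannot be reconciled by assigning them to different times.

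2. **Exceptions.** The ban has none, and the zoster sentence is not worded as one.

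3. **What each sentence leaves open.** Under the ban, the zoster vaccines a site may use are the non-live ones only. The zoster sentence compares two classes, non-live and live, and prefers the first. If live products are excluded, there is nothing to rank second and the comparison is empty. If the comparison means something, the ban is not absolute.

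4. **The availability parenthesis.** In "other non-live vaccine (if available) is preferred over live vaccines" the parenthesis can be read in two ways.
   - It may qualify every non-live option, Shingrix included. A live product then becomes the implied fallback when none can be had.
   - It may qualify only the alternatives to Shingrix, meaning another non-live product if one exists. The parenthesis then creates no fallback.

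   On either reading, the ranking of non-live above live remains. The inconsistency therefore does not depend on which is right.

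5. **The influenza sentence.** "vaccination against influenza virus with inactivated vaccine is preferred" names no live product. It can be read as a preference among vaccines the ban already allows, so it does not conflict with the ban. It is looser than it should be only because it follows the zoster sentence and is linked to it.

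6. **Other sections.** The eligibility criteria (4.2 and 4.3), Other Restrictions and Prohibitions (6.2.2) and the withdrawal rules (8.2) do not mention vaccines. Nothing elsewhere gives an exception to the ban or limits the preference to a time before or after the study.

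7. **Reach of the wording.** Sections 3.3 and 4.1 plan up to 24 sites and up to 24 patients. From Section 3.1, the longest participation is 96 + 12 = 108 weeks. A completer who enrols last has 48 + 12 = 60 weeks. These figures say who is covered by the wording and for how long. They do not estimate how often a live vaccine might be given, and the protocol offers no basis for such an estimate.

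**The case against.** The best defence is that the rule is already clear. The ban is explicit, comes first and has no exception. For a live vaccine to be given, a site would have to prefer an implication to an outright prohibition one sentence earlier. On this view the zoster sentence is loose drafting, and the availability parenthesis may refer only to non-live alternatives to Shingrix.

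Much of this stands. The ban should govern, and the second reading of the parenthesis is a fair one. A reader might infer that the protocol authorises a live zoster vaccine when no non-live product can be found. The documents do not go that far: no sentence grants that permission. A reader might also count the influenza sentence as a second contradiction, but it is compatible with the ban.

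The defence does not remove the words that rank non-live above live. They have no function under the ban, and they address the very situation in which a site would look for guidance.

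It is also fair to object that the practical consequence is unknown. The documents do not say how many patients would need zoster vaccination, and they give no sign that any site lacks a non-live product. That limits the priority of the point. It does not make the two sentences consistent.

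**Conclusion.** The zoster sentence in Section 6.2.1.4 is inconsistent with the ban that precedes it and is wrong as written. This is a minor defect in a safety rule and should be corrected at the next amendment. The conclusion rests on one assumption: that the sponsor means the ban as stated.

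Two larger inferences are not supported. The first is that patients face a demonstrated hazard. The protocol gives no reason for the ban, and Section 1.6 describes selective immunoproteasome inhibition, on preclinical evidence, as modulating immunity and not suppressing it. No risk from a live vaccine can be quantified from these documents. The second is that the results would be affected. Section 10 describes a descriptive study without hypothesis testing, and no endpoint or analysis-set definition refers to vaccination. A per-protocol set is optional and would take account of deviations, but nothing says that a vaccination would decide membership of it.

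**What to change.** In the zoster sentence, keep the opening condition ("If vaccination against herpes zoster is required during the study") and replace the rest with: *only a non-live vaccine (eg, Shingrix) may be given.*

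For consistency, reword the influenza sentence: *Similarly, only a non-live influenza vaccine may be given; inactivated vaccine is preferred.* This keeps the existing preference. It should not be tightened to inactivated vaccine only, because that would exclude any non-live influenza vaccine not classed as inactivated, which the protocol does not now prohibit.

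If the sponsor does intend a live zoster vaccine as a fallback, it should instead be written as an explicit exception to the ban.

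The cost is two reworded sentences in the next amendment. No new data are needed, since vaccinations are already recorded in the eCRF. The only downside is that a patient without access to a non-live zoster vaccine must wait until after the study, and the ban as it stands already requires that.

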6.2.2. Other Restrictions and Prohibitions

For patients requiring surgery, or for any planned surgery during the study, the Medical Monitor should be consulted to discuss KZR-616 dosing.

7. STUDY EVALUATIONS

7.1. Schedule of Assessments

The Schedule of Assessments is presented in [Table 1](#), and the Schedule of KZR-616 Administration (with vital signs and pregnancy testing) is presented in [Table 2](#).

On-site study visits will occur at Weeks 12, 24, 36, 48, 60, 72, 84, and 96, and the EOS Visit. At these visits, safety and efficacy assessments will be performed and KZR-616 will be administered according to the Schedule of Assessments ([Table 1](#)). All other study visits may occur either at the site or at patients' homes via home health providers ([Table 2](#)).

7.1.1. Unscheduled Visits

All attempts should be made to keep patients on the study schedule. Unscheduled visits may be necessary to repeat testing following abnormal laboratory results, for follow-up of AEs, or for other reasons, as warranted. During an unscheduled visit, information regarding concomitant medications and AEs (at a minimum) will be collected. Any of the other procedures listed for the Week 24 visit may also be performed at the Investigator's discretion.

7.1.2. Telehealth Visits

While the study visits in [Table 1](#) are mandatory, in recognition of constraints imposed by the SARS-CoV-2 pandemic, sites may elect to use a combination of telemedicine (as permitted by their institutions) and/or home health providers to conduct these visits. All other visits, including weekly KZR-616 injections, may occur at the site or at patients' homes via home health providers.

For telehealth visits, a limited physical examination will be performed and the MMT-8 will not be assessed. All other assessments should be performed, if feasible. Samples for clinical laboratory assessments will be collected by home health providers and sent to the central laboratory.

Please refer to [Sections 7.2.4, 7.2.6.1, 7.2.6.2, and 7.2.6.3](#) for additional information regarding assessments performed at telehealth visits.

Table 1 Schedule of Assessments

Study Period	Screening/ Baseline ^a	Open-Label Treatment								96/EOT /ETV	97/EOS
		12	24	36	48	60	72	84			
Visit Number	1										
Start of Week	1	12	24	36	48	60	72	84	96	108	
Day ± Window (Days)	1	78±14	162±14	246±14	330±14	414±14	498±14	582±14	666±14	750±14	
Informed consent ^a	X										
Informed consent for genotyping ^b	X										
Inclusion/exclusion criteria ^c	X										
Demographic data ^d	X										
Medical history (including procedures, prior therapy, social history) ^d	X										
Concomitant therapy	X	← →									
Pregnancy test ^e	X ^f	X	X	X	X	X	X	X	X	X	
Physical examination	X ^f	X	X	X	X	X	X	X	X	X	
Vital signs ^g	X ^f	X	X	X	X	X	X	X	X	X	
Weight	X ^f		X		X		X		X	X	
12-lead ECG ^h	X ^f										
MMT-8 ⁱ	X ^f	X	X	X	X	X	X	X	X	X	
MDAAT, MDGIC ⁱ	X ^f	X	X	X	X	X	X	X	X	X	
FI-2 (dominant side only) ⁱ	X ^f		X		X		X		X	X	
Sit-to-stand test ⁱ		X	X	X	X	X	X	X	X	X	
MDI ⁱ					X				X		
CDASI ^{ij}	X ^f	X	X	X	X	X	X	X	X	X	
PtGADA, HAQ-DI, PGIC ^k	X ^f	X	X	X	X	X	X	X	X	X	
EQ-5D-5L ^k	X ^f	X	X	X	X	X	X	X	X	X	
PtGADD ^k	X ^f	X	X	X	X	X	X	X	X	X	
Peak Pruritus NRS ^{jk}	X ^f	X	X	X	X	X	X	X	X	X	

Study Period	Screening/ Baseline ^a	Open-Label Treatment									
Visit Number	1	12	24	36	48	60	72	84	96/EOT /ETV	97/EOS	
Start of Week	1	12	24	36	48	60	72	84	96	108	
Day ± Window (Days)	1	78±14	162±14	246±14	330±14	414±14	498±14	582±14	666±14	750±14	
Hematology, chemistry, CRP, and aldolase ^b	X ^f	X	X	X	X	X	X	X	X	X	
Total IgG			X						X ^m	X	
Cytokines/proteomics ^b	X ^f	X	X	X	X	X	X	X	X	X	
Gene expression (RNA) ^b	X ^f	X	X	X	X	X	X	X	X	X	
KZR-616 administration ^b	X ^q	X	X	X	X	X	X	X	X ^r		
Adverse events	← →										

Abbreviations: CDASI=Cutaneous Dermatomyositis Disease Area and Severity Index; CRP=C-reactive protein; DM=dermatomyositis; DNA=deoxyribonucleic acid; ECG=electrocardiogram; EOS=End of Study; EOT=End of Treatment; EQ-5D-5L=EuroQoL 5-dimension 5-level; ETV=Early Termination Visit; FI-2=Functional Index-2; HAQ-DI=Health Assessment Questionnaire-Disability Index; hCG=beta-human chorionic gonadotropin; IgG=immunoglobulin G; MDAAT=Myositis Disease Activity Assessment Tool; MDI=Myositis Damage Index; MDGIC=Physician Global Impression of Change; MMT-8=Manual Muscle Testing-8 Muscle Groups; NRS=numerical rating scale; PD=pharmacodynamics; PROM=patient-reported outcome measure; PtGADA=Patient Global Assessment of Disease Activity; PtGADD=Patient Global Assessment of Disease Damage; PGIC=Patient Global Impression of Change; RNA=ribonucleic acid

a Patients will be evaluated for eligibility at, or within 8 weeks after, the Week 32 Visit of Study KZR-616-003. Informed consent must be signed prior to any study-related activity in KZR-616-003E. The KZR-616-003 Week 32 Visit may also serve as Visit 1 (Day 1) for the open-label extension study. Assessments at this visit performed as part of Study KZR-616-003 will be used as baseline values for the extension study; therefore, these assessments must be performed prior to the first dose of open-label KZR-616.

b Patients who provide additional informed consent will undergo blood sampling for genetic analysis.

c Eligibility criteria for this study should be assessed only after the Week 32 assessments for Study KZR-616-003 have been completed and informed consent for Study KZR-616-003E has been signed. All data except central laboratory results from samples drawn at that visit should be used to confirm patient eligibility.

d Data from Study KZR-616-003 will be used.

e Women of childbearing potential only. Positive urine pregnancy tests will be confirmed with a serum hCG test.

f Assessments done as part of the Week 32 Visit of Study KZR-616-003.

g Vital signs will be collected prior to dosing. Blood pressure and pulse rate should be collected after the patient has been resting for at least 5 minutes in the seated position. If the blood pressure is elevated on the first measurement at Screening/Baseline, it should be repeated after at least an additional 5 minutes of rest. It is recommended that blood pressure be measured using the same arm at each assessment.

h 12-lead ECG should be performed after the patient has been resting for at least 5 minutes in the supine position.

i Should be completed by qualified personnel, and it is recommended that the same individual performs the assessment at all visits. Chest radiograph and ECG (as well as other assessments approved by the Medical Monitor) may be performed as needed to confirm findings requiring confirmation on the MDAAT.

- j Should be performed only in patients with DM.
- k It is recommended that PROMs are completed first at each visit where performed (ie, prior to any other procedures or assessments other than signing of informed consent).
- l See [Section 7.2.6.4](#) for assessments.
- m Only for the ETV.
- n Blood sampling for cytokines and proteomics will be performed prior to dosing.
- o Samples will be collected prior to dosing in patients who have provided the proper informed consent for genetic analyses.
- p Patients will receive study drug weekly according to [Table 1](#) and [Table 2](#). At-home administration by the patient or caregiver may be an option for patients deemed appropriate by the Investigator (see [Section 5.4](#)). Home health providers will be arranged for patients who choose not to return to the site or administer study drug at home.
- q The Week 32 assessments from Study KZR-616-003 must be performed, and informed consent for this open-label extension study signed prior to the first dose of open-label KZR-616.
- r Does not apply to the ETV.

Table 2 Schedule of KZR-616 Administration and Assessments

Visit No.	2	3	4	5	6	7	8	9	10	11
Start of Week	2	3	4	5	6	7	8	9	10	11
Day ± Window (Days)	8±1	15±1	22±1	29±1	36±1	43±1	50±1	57±1	64±1	71±1
Vital signs ^a			X				X			
Urine pregnancy testing ^b			X				X			
KZR-616 administration	X	X	X	X	X	X	X	X	X	X

Visit No.	13	14	15	16	17	18	19	20	21	22	23
Start of Week	13	14	15	16	17	18	19	20	21	22	23
Day ± Window (Days)	85±1	92±1	99±1	106±1	113±1	120±1	127±1	134±1	141±1	148±1	155±1
Vital signs ^a				X			X				
Urine pregnancy testing ^b				X			X				
KZR-616 administration	X	X	X	X	X	X	X	X	X	X	X

Visit No.	25	26	27	28	29	30	31	32	33	34	35
Start of Week	25	26	27	28	29	30	31	32	33	34	35
Day ± Window (Days)	169±1	176±1	183±1	190±1	197±1	204±1	211±1	218±1	225±1	232±1	239±1
Vital signs ^a				X			X				
Urine pregnancy testing ^b				X			X				
KZR-616 administration	X	X	X	X	X	X	X	X	X	X	X

Visit No.	37	38	39	40	41	42	43	44	45	46	47
Start of Week	37	38	39	40	41	42	43	44	45	46	47
Day ± Window (Days)	253±1	260±1	267±1	274±1	281±1	288±1	295±1	302±1	309±1	316±1	323±1
Vital signs ^a				X			X				
Urine pregnancy testing ^b				X			X				
KZR-616 administration	X	X	X	X	X	X	X	X	X	X	X

Visit No.	49	50	51	52	53	54	55	56	57	58	59
Start of Week	49	50	51	52	53	54	55	56	57	58	59
Day ± Window (Days)	337±1	344±1	351±1	358±1	365±1	372±1	379±1	386±1	393±1	400±1	407±1
Vital signs ^a				X				X			
Urine pregnancy testing ^b				X				X			
KZR-616 administration	X	X	X	X	X	X	X	X	X	X	X

Visit No.	61	62	63	64	65	66	67	68	69	70	71
Start of Week	61	62	63	64	65	66	67	68	69	70	71
Day ± Window (Days)	421±1	428±1	435±1	442±1	449±1	456±1	463±1	470±1	477±1	484±1	491±1
Vital signs ^a				X				X			
Urine pregnancy testing ^b				X				X			
KZR-616 administration	X	X	X	X	X	X	X	X	X	X	X

Visit No.	73	74	75	76	77	78	79	80	81	82	83
Start of Week	73	74	75	76	77	78	79	80	81	82	83
Day ± Window (Days)	505±1	512±1	519±1	526±1	533±1	540±1	547±1	554±1	561±1	568±1	575±1
Vital signs ^a				X				X			
Urine pregnancy testing ^b				X				X			
KZR-616 administration	X	X	X	X	X	X	X	X	X	X	X

Visit No.	85	86	87	88	89	90	91	92	93	94	95
Start of Week	85	86	87	88	89	90	91	92	93	94	95
Day ± Window (Days)	589±1	596±1	603±1	610±1	617±1	624±1	631±1	638±1	645±1	652±1	659±1
Vital signs ^a				X				X			
Urine pregnancy testing ^b				X				X			
KZR-616 administration	X	X	X	X	X	X	X	X	X	X	X

Abbreviations: hCG=beta-human chorionic gonadotropin

NOTE: Patients will receive study drug weekly according to [Table 1](#) and [Table 2](#). At-home administration by the patient or caregiver may be an option for patients deemed appropriate by the Investigator (see [Section 5.4](#)). Home health providers will be arranged for patients who choose not to return to the site or administer study drug at home.

- a Vital signs will be collected prior to dosing. Blood pressure and pulse rate should be collected after the patient has been resting for at least 5 minutes in the seated position. It is recommended that blood pressure be measured using the same arm at each assessment.
- b Women of childbearing potential only. Positive urine pregnancy tests will be confirmed with a serum hCG test.

